### 7.7.3. Randomization

Subjects that meet all inclusion and exclusion criteria will be randomized to one of two treatment groups in a 1:1 ratio for each study center according to a predetermined computer-generated randomization code.

Subjects will be randomized to treatment using an IWRS. The randomization scheme will include age stratum at 3 levels ( $\geq 2$  to  $< 12$ ,  $\geq 12$  to  $< 18$  or  $\geq 18$ ) and investigative site.

### 7.7.4. Analysis Populations

The ‘Intent-to-Treat’ (ITT) analysis population will include all randomized subjects. The ITT population will be the primary population for all efficacy analyses.

The “All-treated” analysis population will consist of all subjects receiving at least one application of study drug. All safety analyses will be performed on the all-treated population.

The Per-Protocol (PP) population will include all subjects in the ITT population who complete 6 weeks of treatment and 12 weeks of post-treatment efficacy evaluation without any major deviations from the protocol. The subjects to be included in the PP analysis population will be determined by the Sponsor prior to the unblinding of the study. The PP population will be secondary for the primary endpoint only.

### 7.7.5. Handling of Missing Data

The primary method of dealing with missing data is multiple imputations (MI). Last Observation Carried Forward (LOCF) and Baseline Observation Carried Forward (BOCF) will be used as sensitivity analyses.

For the multiple imputations, twenty sets of imputed data will be generated. These will be imputed using SAS Proc MI as shown below.

```
Proc MI NIMPUTE=20 SEED=861879112 ROUND=....111111  
      MINIMUM=....100000 MAXIMUM=....666666;  
      class treat site sex agegrp;  
      var treat site sex agegrp w0 w2 w4 w6 w12 w18;  
      fcs logistic(treat) logistic(site) logistic(sex) logistic(agegrp) reg(w0) reg(w2)  
      reg(w4) reg(w6) reg(w12) reg(w18);  
      run;
```

Where:

treat = study treatment (CLS006, Vehicle)  
site = investigative site  
sex = sex (male, female)

agegrp = age group ( $\geq 2$  to  $< 12$ ,  $\geq 12$  to  $< 18$  or  $\geq 18$ )

w0 = number of warts at baseline (total number to be treated during the study)

w2 = number of remaining treated warts at Week 2

w4 = number of remaining treated warts at Week 4

w6 = number of remaining treated warts at Week 6

w12 = number of remaining treated warts at Week 12

w18 = number of remaining treated warts at Week 18

Note: Variable names may differ from those used in the actual programs, but the methodology will be the same.

If an imputed value is not within the appropriate range after the default of 100 tries, the SAS Proc MI option MINMAXITER may be increased in order to impute appropriate values.

In general, data will not be imputed for safety analysis.

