A follow-up phase II study [REDACTED] was also conducted in [REDACTED] to explore the efficacy and safety of the [REDACTED] Topical Gel (CLS003) as well as single-agents Furosemide Topical Gel 0.125% w/w (CLS006) and [REDACTED] Topical Gel 0.125% w/w for treatment of cutaneous warts. This was a randomized, double-blind, vehicle-controlled study in 80 subjects who were treated with study product daily for 42 days with an 8-week follow-up period. All active treatment groups (combination and single-agent) showed effects on wart size including statistically significant reductions in dimensions of all treated warts, and substantial effects on wart clearance. No serious adverse events (SAEs), discontinuations due to AEs, or deaths occurred during the study. All AEs were of mild (n=53) or moderate severity (n=2) and self-limiting without therapeutic intervention. The AE profile was similar for all subjects across treatment groups. Most treatment-emergent adverse events (TEAEs) were considered as unlikely related or unrelated (n=47) to treatment. Common TEAEs in the single-agent furosemide treated group included influenza-like illness and upper respiratory tract infections which occurred in 2 / 20 (10%) subjects. No clinically significant changes were attributable to treatment in any of the three investigational products for hematology, clinical chemistry, urinalysis, vital signs, or ECG parameters. Overall, the safety profile of the investigational products containing single-agent furosemide or [REDACTED] applied for 42 days supports the use of Furosemide Topical Gel 0.125% w/w (CLS006) for the treatment of nongenital cutaneous warts.

Based upon the favorable risk/benefit outcomes to date, two larger Phase 3 studies of Furosemide Topical Gel 0.125% w/w (CLS006) will be conducted to validate the Phase 2 results of the single-agent furosemide product for the treatment of nongenital cutaneous common warts (*verruca vulgaris*) and to support a new drug application (NDA) submission.

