#### 7.4.1.2. Wart Size

The size of each Baseline Treatment Wart will be measured in millimeters (mm) using a standardized ruler. The longest dimension (diameter) on the epidermal plane of the skin will be recorded.

- **In order to prevent inter-evaluator variability, it is important that the same evaluator measure the subject's wart(s) at baseline and at all subsequent study visits, whenever feasible.**

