### 7.7.2. Sample Size Determination

The sample size estimates for the current study are based upon the rates of clearance of warts in the previous Phase 2 study [REDACTED]. This was a randomized, double-blind, vehicle-controlled, Phase II study in 80 subjects who were treated with topical [REDACTED], furosemide, [REDACTED], or vehicle for 42 days daily with an 8-week follow-up period. For the furosemide treatment group, the proportion of subjects with all cleared warts was 0.1 (10%) versus 0 in the vehicle.

The difference in the proportion of subjects with all treated warts cleared (complete clearance) at the Week 18/End of Post-treatment Efficacy Evaluation period (is the primary endpoint of the current study. For conservative purposes, assuming 10% and 2% complete clearance rates in the furosemide and vehicle treated groups respectively 200 subjects randomized per treatment group will provide for 92% power at a two-sided  $\alpha$  of 0.05 to detect a difference between active and placebo.

With the inclusion of an additional 80 subjects in the  $\geq 2$  to  $< 12$  cohort, the total sample size of 480 will provide 96% power with the assumption unchanged.

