## 12.5.2 Methods for Handling Dropouts and Missing Data

The frequency and percentage of missing values for each variable will be reported.

The primary method of dealing with missing data will be fully conditional specification (FCS) multiple imputations (MI; also called multiple imputation by chained equation [MICE]).

FCS MI relaxes the assumption of joint multivariate normality of all variables. FCS MI specifies the multivariate imputation model on a variable-by-variable basis on a set of conditional densities, one for each incomplete variable. Buuren, et al (2011) and Lee and Carlin (2012) provide results from simulation studies that suggest that FCS MI generally yields estimates that are unbiased with proper standard errors and provide appropriate coverage when data are missing at random (MAR).

For the multiple imputations, twenty sets of imputed data will be generated. These will be imputed using SAS Proc MI as shown below.

```
Proc MI NIMPUTE=20 SEED=861879112 ROUND=....111111  
      MINIMUM=....1000000 MAXIMUM=....666666;  
      class treat site sex agegrp;  
      var treat site sex agegrp w0 w2 w4 w6 w12 w18;  
      fcs logistic(treat) logistic(site) logistic(sex) logistic(agegrp) reg(w0) reg(w2)  
      reg(w4) reg(w6) reg(w12) reg(w18);  
      run;
```

Where:

treat = study treatment (CLS006,  
Vehicle) site = investigative site  
sex = sex (male, female)  
agegrp = age group ( $\geq 2$  to  $< 12$ ,  $\geq 12$  to  $< 18$  or  
 $\geq 18$ )  
w0 = number of warts at baseline (total number to be treated during the study)  
w2 = number of remaining treated warts at Week 2  
w4 = number of remaining treated warts at Week 4  
w6 = number of remaining treated warts at Week 6  
w12 = number of remaining treated warts at Week 12  
w18 = number of remaining treated warts at Week 18

Note: Variable names may differ from those used in the actual programs, but the methodology will be the same.

If an imputed value is not within the appropriate range for each variable in the model after the default of 100 tries, the SAS Proc MI option MINMAXITER may be increased in order to impute appropriate values.

The PROC FREQ procedure will be used to perform the *Cochran–Mantel–Haenszel test* and

---

will take the output dataset created from the MI procedure described above.

```
*** Obtain Mantel-Haenszel estimates ***;  
PROC FREQ data=imputed;  
  table site*agegrp*treat*response / cmh;  
  ODS OUTPUT cmh=cmh;  
  by _imputation_;  
RUN;
```

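### The primary imputation model omits the wart size measured at every visit, so it cannot tell drop-outs with nearly cleared warts from those with unchanged ones

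*Protocol*

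**What the plan says.** Protocol 7.7.5 and SAP 12.5.2 give the same model for the primary endpoint: twenty chained-equation imputations with "var treat site sex agegrp w0 w2 w4 w6 w12 w18", where the w variables count the treated warts still present. The Week 18 count is imputed by normal regression, rounded to a whole number and held between 0 and 6. No size variable appears.

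Size is collected. Protocol 7.4.1.2 states: "The size of each Baseline Treatment Wart will be measured in millimeters (mm) using a standardized ruler". The same section asks for the same evaluator at baseline and all later visits, and has clinical clearance recorded as 0 mm. The schedule in Protocol 7.3.1 places wart assessments at every efficacy visit.

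The SAP supports its method with published simulations in which chained-equation imputation will "provide appropriate coverage when data are missing at random (MAR"). LOCF and BOCF are sensitivity analyses for the primary endpoint. Lack of efficacy is one of the listed reasons for discontinuation in Protocol 7.2.3. No drop-out rate is given.

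**The concern.** A wart scores 1 in the count whether it has shrunk to 1 mm or still measures 10 mm, so the count is a coarse reading of the scale on which clearance is recorded. Two drop-outs in the same arm with the same counts, site, sex and age group get the same predicted chance of clearing, even if one is almost clear and the other unchanged.

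Missing at random is a condition given the variables in the model. If subjects who see no shrinkage leave more often, missingness depends on a collected variable that the model does not contain, and the assumption is weaker than it need be. The sponsor already treats size as a response measure: reduction in wart size is a tested secondary endpoint, and Protocol 5.2 reports Phase 2 "statistically significant reductions in dimensions of all treated warts".

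At stake are the clearance rates in both arms and the precision of the primary test. SAP 12.5.5 also applies multiple imputation to complete clearance at Weeks 12 and 6, so the omission reaches other tests in the fixed sequence.

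**Working it through.** **The plan's own figure.** Inputs from Protocol 7.7.2: "assuming 10% and 2% complete clearance rates in the furosemide and vehicle treated groups respectively", two-sided 0.05, 1:1 allocation. With the pooled-variance formula, power = Φ{[0.08 − 1.96·√(2·0.06·0.94/n)] / √((0.10·0.90 + 0.02·0.98)/n)}.
- n = 200: (0.08 − 0.0465)/0.0234 = 1.43, power 92.4% (stated 92%).
- n = 240: (0.08 − 0.0425)/0.0214 = 1.755, power 96.0% (stated 96%).

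The stated power reproduces, with no allowance for missing data.

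**Simulations.** The documents give neither a drop-out rate nor a size–clearance relation. Wart-count and size trajectories were therefore assumed, calibrated to about 10% v 2% clearance.

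*Simulation A* (60,000 per arm; 13–15% drop-out after Week 6 or 12; log-odds of drop-out rising by 1–2 per SD of percent size remaining). With the plan's regression, clearance is overstated by 0.8–0.9 points (CLS006) and 1.0–1.4 (vehicle). With total size added, the excess is 0.3–0.5 and 0.7–0.8. Adding size moves the treatment difference by at most about 0.2 points.

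*Simulation B* (trials of 480; drop-out after Week 6; unshrunk means relative Week 6 size above the median; leaving probability 25% v 5% by shrinkage). Results with the plan's regression:

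| Who leaves more | Arm | Drop-out | Cleared among drop-outs: true / plan / with size | Whole arm: true / plan / with size |
|---|---|---|---|---|
| Unshrunk | Vehicle | 17.9% | 0.5 / 6.1 / 4.5% | 1.7 / 2.7 / 2.4% |
| Unshrunk | CLS006 | 12.3% | 4.3 / 10.6 / 7.3% | 10.2 / 10.9 / 10.5% |
| Shrunk | Vehicle | 12.3% | 4.3 / 6.7 / 10.5% | 2.0 / 2.3 / 2.7% |
| Shrunk | CLS006 | 17.9% | 14.4 / 9.7 / 12.8% | 10.1 / 9.3 / 9.8% |

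The arm shift is the drop-out rate times the excess among drop-outs. When unshrunk subjects leave more, vehicle gives 0.179 × (6.1 − 0.5) = 1.0 point and CLS006 gives 0.123 × (10.6 − 4.3) = 0.8 point. The difference is 10.9 − 2.7 = 8.2 points under the plan and 10.5 − 2.4 = 8.1 with size, against a true 10.2 − 1.7 = 8.5.

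With drop-out unrelated to size, the plan's model imputes 6.4% (vehicle) and 9.9% (CLS006) of unshrunk drop-outs as cleared, when truly about 0% clear; with size these fall to 3.8% and 5.0%. Shrunk CLS006 drop-outs are imputed too rarely: 10.4% against 16.0%.

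*Simulation C* (other assumed trajectories, 8–14% drop-out, plan's regression). When unshrunk subjects leave more, adding size lowers imputed clearance among drop-outs from 10.5% to 3.8% (CLS006, true 1.2%) and from 6.6% to 3.0% (vehicle, true 0.3%). Misclassification of drop-outs also falls when drop-out is unrelated to size.

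**Separating the omission from the model form.** Replacing the rounded normal regression in B by a logistic model for clearance, with CLS006 against truth in each case:
- Random drop-out, no size: 10.4% v 10.0% (vehicle 2.0% v 2.1%), no net bias.
- Unshrunk leave more, no size: 11.0% v 4.2% (vehicle 2.4% v 0.6%); with size 4.2% and 0.6%.
- Shrunk leave more, no size: 9.5% v 14.4% (vehicle 1.7% v 3.9%); with size 14.1% and 3.7%.

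So the sign of the omission's effect follows the drop-out mechanism. With the plan's regression and random drop-out, vehicle drop-outs are imputed as cleared at 6.6% without size and 6.8% with it, against 2.4% true; that excess comes from the model form.

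**Power, illustrative.** An equal excess of 3–10 points among 5–20% drop-outs raises each arm by 0.05 × 3 = 0.15 to 0.20 × 10 = 2.0 points. With the difference held at 8 points, power at 240 per arm falls from 96.0% to between 95.7% and 90.0%. This counts the whole excess, whatever its source.

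**Noise.** In one scenario of A with drop-out unrelated to size, p(1 − p) for CLS006 drop-outs falls from 0.074 to 0.042 when size is used. With 14% drop-out this is 240 × 0.14 × 0.032 = 1.1, against a complete-data variance of 240 × 0.10 × 0.90 = 21.6: about 5% of the variance, or 2.5% of the standard error.

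**The case against.** The drop-out mechanism is assumed. Lack of efficacy is one entry in an open list without frequencies, and nothing says that subjects judge it by wart size. This stands, and the direction of bias has to be stated as conditional.

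A reader might infer that the plan is biased in favour of CLS006. The logistic model without size does widen the gap among drop-outs (11.0 − 2.4 = 8.6 points against 4.2 − 0.6 = 3.6 true), but the plan does not use that model. Under its own regression the vehicle arm is overstated at least as much as CLS006, and the difference, if anything, shrinks.

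A reader might also infer that the Phase 2 response lay mainly in size. The same sentence in Protocol 5.2 also reports substantial effects on clearance, and the 10% in Protocol 7.7.2 counts only subjects with every wart cleared, so it says nothing about partial clearance.

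LOCF and BOCF leave a drop-out with remaining warts as not cleared, so they show whether the result leans on imputed clearances. They do not use size and do not repair the primary analysis. Early-termination assessments after Week 6 share the Week 18 visit, and the SAP applies no visit windows, so some may supply the Week 18 value; missingness could then be lower than simulated.

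Finally, adding size is not a full cure. With the plan's regression in Simulation B, it gave no gain for vehicle under random drop-out and a larger vehicle excess when shrunk subjects left more. That stands too.

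**Conclusion.** The point holds as a conditional weakness with an inexpensive remedy. The model leaves out a collected variable on the very scale that defines clearance, and so misallocates imputed clearance between unshrunk and shrunken drop-outs whatever the drop-out mechanism.

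The net effect depends on who leaves. If unshrunk subjects leave more, clearance is overstated by roughly 0.7–1.4 points per arm. Adding size removes some 0.3–0.6 of that (comparing the ranges with and without size); the rest belongs mainly to the truncated, rounded normal form. If drop-out is unrelated to size, the omission mainly costs precision. If shrunk subjects leave more, its effect reverses, although the rounding excess can still leave the vehicle arm overstated.

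Adding size changes the treatment difference by only about 0.1–0.2 points against the planned 8. No bias towards CLS006 should be claimed for the plan as written. All these sizes rest on assumed trajectories, drop-out rates and mechanisms.

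**What to change.** In Protocol 7.7.5 and SAP 12.5.2, add the total size in mm of the Baseline Treatment warts at baseline and Weeks 2, 4, 6 and 12 to the VAR statement, each with a regression term. Week 18 size adds little, since it is normally missing when the Week 18 count is.

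Extend ROUND, MINIMUM and MAXIMUM so that each has one entry per variable. Use 0 as the minimum for size. Set the maximum from the plausible total diameter: the entry criteria cap it at 6 × 10 = 60 mm at baseline, and later visits need room for growth. As printed, the SAP's MINIMUM string already has one entry more than the ten variables, so check it at the same time. State that imputed size is set to 0 when the imputed count is 0.

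Keep size as a predictor in any revised clearance model. One suited to a bounded count or binary outcome would address the excess that size alone does not remove.

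The cost is a few lines of code and SAP text, with no new data. The downsides are more correlated regressors, possibly a higher MINMAXITER (which the plan already allows), and extra noise in total size where warts cluster or merge.

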## **7.7.6. Efficacy Endpoints**

### **7.7.6.1. Primary Endpoint**

The primary analysis of efficacy will be made on the difference in the proportion of subjects with complete clearance of all treated warts (i.e., Baseline/Treated warts) between the active and vehicle at Week 18 /End of Post-treatment Efficacy Evaluation. This comparison will be made using a CMH test stratified by age group ( $\geq 2$  to  $< 12$ ,  $\geq 12$  to  $< 18$  or  $\geq 18$ ) and investigative site.

### **7.7.6.2. Secondary Endpoints**

Secondary efficacy analyses will be conducted sequentially as follows:

- The ratio of cleared warts to all treated warts at Week 18/End of Post-treatment Efficacy Evaluation.
- Difference in the proportion of subjects with complete clearance of all treated warts at Week 12, then Week 6/EOT.
- The ratio of cleared warts to all treated warts at Week 12, then Week 6/EOT.
- Comparisons of reduction from baseline in wart size of treated warts at Week 18/End of Post-treatment Efficacy Evaluation.

To control type-1 error, the statistical testing will stop if non-significant superiority of active to vehicle ( $p > 0.025$  one-sided) is observed for any of the primary or secondary endpoints.

### **7.7.6.3. Tertiary Endpoints**

- All endpoints will be compared at all other time-points.

- Evaluation of durability of response (clearance and/or wart size reduction) and incidence of recurrence of treated warts from Week 18/End of Post-treatment Efficacy Evaluation period to the end of the follow-up period (week 30).

These data are considered tertiary and exploratory to gain insight regarding the pharmacodynamic nature of the treatment response. No formal hypothesis testing is planned. Therefore, any statistical testing done will be considered to be descriptive and not inferential.

#### **7.7.7. Efficacy Analysis**

Comparisons of proportions of subjects with all treated warts cleared will be made using Cochran-Mantel-Haenszel (CMH) test for treatment stratified by age group ( $\geq 2$  to  $< 12$ ,  $\geq 12$  to  $< 18$  or  $\geq 18$ ) and investigative site at  $\alpha = 0.05$ . Because of the low complete clearance rate, sites will be pooled in a manner ensuring that each pooled site will have sufficient number of subjects cleared for a stratified CMH analysis. The algorithm for pooling sites will be described in the SAP and finalized prior to unblinding. Comparisons of clearance rates of treated warts (number of cleared warts/number of treated warts) will be made using two-sided Wilcoxon rank sum testing at  $\alpha = 0.05$ .

For the continuous variables of wart size (diameter), analysis of covariance (ANCOVA) will be used to test CLS006 versus vehicle at Week 6/EOT, Week 18/End of Post-treatment Efficacy Evaluation and each week of the Post-treatment Efficacy Evaluation period and Follow-up period using a mixed effects model with site, age group ( $\geq 2$  to  $< 12$ ,  $\geq 12$  to  $< 18$  or  $\geq 18$ ) and Baseline Treatment Wart size (i.e., diameter) as covariates (baseline wart size will be used as a covariate for comparison of wart size).

Data listings and averages will be presented for safety measures.

#### **7.7.8. Safety Endpoints**

Safety variables including AEs, vital signs, and laboratory parameters will be collected according to the Schedule of Visits and Study Assessments (refer to Section 7.3.1).

#### **7.7.9. Safety Analysis**

Safety variables will be tabulated and presented for all patients in the Safety population. AEs will be categorized by system organ class and Preferred Term from the current version of MedDRA. AEs will be summarized overall, by seriousness, severity, and relationship to treatment. Incidence of AEs will be presented overall, by system organ class and preferred term. Severity and relationship to study drug of the incidence of AEs will also be presented. AEs causing study drug withdrawal and/or early study discontinuation and incidence of SAEs will be summarized.

Changes from baseline in vital signs and laboratory parameters, and shifts from baseline in laboratory parameters will be summarized by treatment. Descriptive statistics and frequency tables will be prepared as appropriate for laboratory measurements.

### **7.7.10. Multicenter Pooling**

Approximately 40 centers are planned in this study; whenever possible, approximately at least 12 subjects will be enrolled per center. In the event a center has a low number of subjects enrolled or an insufficient number of subjects with complete clearance for the stratified CMH analysis, pooling of centers will be performed based on geographical center location. The algorithm for pooling of centers will be described in the Statistical Analysis Plan. Descriptive summary statistics will be generated including center and pooled-center (when appropriate) by primary and secondary efficacy endpoints.

## **8. ETHICS AND GENERAL STUDY CONDUCT CONSIDERATIONS**

### **8.1. ETHICAL CONDUCT OF THE STUDY**

This study will be conducted in accordance with the FDA and ICH guidelines on current GCP following the ethical principles originating from Declaration of Helsinki. Additionally, the study will be conducted in accordance with any applicable laws or regulations of the country in which the clinical research is conducted.

